3.0 Intervention to be studied

- Each of the drugs used in this study have been FDA approved for the adult population. Although not approved for pediatric patients, they are commonly used as part of standard practice for pediatric analgesia and well-studied.
- One group of subjects will receive intrathecal morphine: spinal (neuraxial) dose of preservative free morphine (Duramorph), usually about 4-5mcg/kg. This is injected into the cerebrospinal fluid under sterile technique by a pediatric anesthesiologist while the subject is already under general anesthesia. This procedure is well-described in the pediatric population and used regularly for postoperative pain relief for a variety of procedures including open lower abdominal procedures.
- The second group of subjects will have bilateral quadratus lumborum blocks: peripheral nerve block utilizing ropivacaine 0.2%, usually about $\frac{1}{2}$ mL per/ kg per side (total dose approximately 1mL/kg). This is injected in the subject's flank in the fascial plane between the quadratus lumborum muscle and the psoas muscle. Ultrasound guidance is used for needle and structure localization and this procedure is done by a pediatric anesthesiologist while the subject is already under general anesthesia. Quadratus lumborum blocks are regularly used in clinical practice for postoperative pain relief for a variety of open lower abdominal procedures.

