10.0 Study Design / Methods

- This prospective, randomized, blinded study will attempt to determine if intrathecal morphine provides superior analgesia postoperatively for open lower abdominal procedures when compared to bilateral quadratus lumborum blocks. It will also assess side effects of both pain interventions.
- Once a parent/guardian provide written informed consent, subjects will be assigned a number with a corresponding group. Randomization will be performed by a statistician prior to enrollment and assigned based on the patient's enrollment number. Subjects will be assigned to one of the following groups: 1) Intrathecal Morphine: spinal (neuraxial) dose of preservative free morphine (duramorph), usually about 4-5mcg/kg, or 2) Quadratus Lumborum Block: peripheral nerve block utilizing ropivacaine 0.2%, usually about $\frac{1}{2}$ mL per kg per side (total dose approximately 1mL/kg). The total dose of administered medication (duramorph or ropivacaine) is at the discretion of the anesthesiologist but will be within the dose range as stated above.
- The operating room pharmacist will follow the randomization to prepare or provide the correct medication. Intrathecal morphine will be prepared by the operating room pharmacist. Local anesthetic vials for quadratus lumborum blocks will be obtained from the pharmacy and the medication will be drawn into a syringe by an anesthesiologist who is part of the research team prior to injection. The dosage prepared and administered will be based on weight.
- The pharmacist will not be blinded to the randomization. Nor will the operative team. The study team member who completes data collection from the family and chart review will be blinded to randomization. In addition, the parent and child will also be blinded to the type of block that is used.
- The intervention will be administered in the operating room after the subject is under general anesthesia but prior to incision, as per usual practice. The block will be performed by a study team member board certified in pediatric anesthesiology. Quadratus lumborum blocks are placed using ultrasound guidance, local anesthetic is injected in the fascial plane using aseptic technique. Intrathecal morphine is accomplished by injection of preservative-free morphine in the intrathecal space in the lumbar region using sterile technique.

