- Approximately 24 hours after the procedure, a research team member will ask the parent/guardian about side effects such as nausea, vomiting, itching, etc. The research team member will also ask the family if they were satisfied with the subject's pain control postoperatively and overall experience. If a family member or guardian is not present, a care team member will be asked about side effects and the patient's chart will be reviewed for notes pertaining to side effects.
- The patient's chart will be used to see if and how much narcotic pain medication was administered in the first 48 hours after the procedure as well as documented pain scores up to 48 hours after the procedure ends. The chart medication administration record will also be used to identify administration of rescue medications for nausea

or itching non-opioid medications such as acetaminophen or ibuprofen, or other medications such as diazepam or oxybutynin.

Table 1. Baseline and Intraoperative Assessments	
Demographics	
Baseline	
Pre-op meds including opioids in past 24 hours	
Randomization	
Anesthesia intra-op data	
Surgical techniques	
Adverse Events	

Table 2. Post-Op Follow Up Assessments		
Outcome Measure	Instrument	Collected
Pain Scores	Charted pain scores	24 and 48 hrs. post-op
Pain Control Satisfaction	Parent/Guardian Satisfaction	24-hours post-op
Side Effects Experienced	Parent/Guardian Satisfaction	24-hours post-op
Overall Satisfaction	Parent/Guardian Satisfaction	24-hours post-op
Opioid Consumption	MME Consumption	24 and 48 hrs. post-op
Side Effects and Adverse Events	Adverse Events	Assessed through post-op hours 0-48
Medications	Medications used to control or relieve side effects	24 and 48 hrs. post-op

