18.0 Drugs or Devices

- The intrathecal morphine will be prepared in the pharmacy by a licensed pharmacist under a sterile hood; the local anesthetic for quadratus lumborum block will be drawn immediately preceding the block from a sterile vial in a sterile operating room by a board-certified pediatric anesthesia attending participating in the study.
- The contents of the injectate will be based off the patient's randomly assigned group.
- The pharmacist will not be blinded to the randomization. Nor will the operative team. The study team member who completes data collection from the family and chart review will be blinded to randomization, as well as the child and parent.
- The drugs used in this study, morphine and ropivacaine, are FDA approved for use in this manner for adults; they have not been FDA approved for children, although they are used regularly as part of standard of care. Intrathecal morphine has been shown to

be safe in pediatric patients for major surgeries. In a recent retrospective study by Keskin et al [6], of 100 children who received 5 mcg/kg intrathecal morphine for major surgery for postoperative analgesia there were no serious adverse events (minor side effects of pruritis and nausea/vomiting seen in small number of patients, 14 and 9 patients respectively). An additional retrospective review from CHOP of 187 pediatric patients concluded that ITM in this population is a useful and safe analgesic adjunct [4]. The usage of intrathecal morphine in pediatric patients undergoing major spinal surgery is well established and without report of major adverse events [7,8]. Ropivacaine use is well established in pediatric patients, whether administered neurally (epidural or caudal) or for peripheral nerve block. The European Society of Regional Anesthesia and American Society of Regional Anesthesia published a joint recommendation on local anesthetic use for regional/neuraxial anesthesia in pediatric patients which included dosing strategies for ropivacaine [10].

References

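### Parent and child are said to be blinded to the block, but nothing in the plan masks the different injection sites, so the parent-reported secondary outcomes are open to unblinding.

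*Combined protocol and SAP*

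**What the plan says.** Section 10.0 calls the study blinded and sets out who knows the allocation. On the unblinded side: "The pharmacist will not be blinded to the randomization. Nor will the operative team". On the blinded side: "In addition, the parent and child will also be blinded to the type of block that is used". Section 18.0 repeats the claim: "The study team member who completes data collection from the family and chart review will be blinded to randomization, as well as the child and" the parent.

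The two techniques enter the body at different places. Section 3.0 says "The second group of subjects will have bilateral quadratus lumborum blocks" and, of that block, "This is injected in the subject's flank in the fascial plane between the quadratus lumborum muscle and the psoas muscle". Section 10.0 describes the other arm as "injection of preservative-free morphine in the intrathecal space in the lumbar region using sterile technique". Both are given in the operating room once the child is anesthetised.

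About a day later, "a research team member will ask the parent/guardian about side effects such as nausea, vomiting, itching, etc". At the same contact the family is asked whether they were satisfied with pain control and with the experience overall. If no family member is there, a care team member is asked about side effects and the chart is read for relevant notes.

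**The concern.** The plan asserts that parent and child are blinded but gives no means of keeping them so after the child wakes. One arm is injected on both flanks and the other in the lumbar region. A parent who dresses, turns or washes a child aged 12 months to 11 years (Section 5.0) may notice where a mark or dressing is.

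Two kinds of outcome depend on that parent. Satisfaction is a subjective answer. Itching and nausea in a small child are reported by proxy. The Objectives predict more side effects with ITM, and Section 15.0 lists itching for ITM but not for QL. A parent who believes the child had spinal morphine could therefore report in the direction of the trial's second hypothesis. For satisfaction, the documents give no basis for predicting a direction.

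**Working it through.** **1. Is there a masking mechanism?** Sections 3.0, 9.0, 10.0 and 18.0 were set side by side.

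- During the procedure: yes. The child is anesthetised and in the operating room.
- After the procedure: none is described. There are no matched dressings, no sham puncture, no instruction to staff not to disclose the block, and no check of what parents guessed.
- Ward and care staff: their blinding status is not stated, although a care team member is the fallback source for side effects.

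**2. Which outcomes depend on the parent?** The sources below are from Section 10.0, including Table 2; the status of each outcome is from Sections 4.0 and 12.0.

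| Outcome | Status | Listed source | Open to a parent's belief about the arm |
|---|---|---|---|
| MME/kg, first 24 hours | primary (Section 12.0) | chart | not directly |
| Pain scores | secondary in Section 12.0 | chart | not directly |
| Side effects | secondary | parent at 24 hours; adverse events over 0-48 hours; rescue medication in the administration record | in part |
| Satisfaction with pain control | secondary | family at 24 hours only | yes |
| Overall satisfaction | secondary | family at 24 hours only | yes |

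**3. Denominator.** Section 12.0 gives 12 per group, raised by 15% and then by 10%, to 15 per group.

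- The 12 reproduces: the two-sample t-test size for a difference of 0.1 and SD of 0.076 (two-sided alpha 0.05, 80% power) is 10.12. Dividing by the Mann-Whitney worst-case efficiency of 0.864 gives 11.72, rounded up to 12.
- Adding the inflations gives 12 × 1.25 = 15.0. Compounding them gives 12 × 1.15 × 1.10 = 15.18. Either agrees with the stated 15, and 2 × 15 = 30 agrees with Section 6.0.

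This calculation matters here only because it supplies the denominator.

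**4. What one answer is worth.** For a yes/no item with n children in an arm, k changed answers move that arm's rate by k/n.

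- One answer: 1/15 = 6.7 percentage points.
- Two answers: 2/15 = 13.3 percentage points.
- If only 12 in an arm were analysed: 1/12 = 8.3 points per answer.

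**5. Can an expected bias be computed?** Let r be the share of ITM parents who work out the arm, and d the resulting rise in the chance of reporting a symptom. The expected shift in the ITM rate is r × d. The documents give neither input. Taking d as 20 points purely as an assumption (a yes to itching rising from 20% to 40%):

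- r = 0: 0 points
- r = 0.5: 0.5 × 20 = 10 points
- r = 1: 1 × 20 = 20 points

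The range starts at zero, and nothing in the documents narrows it. This is an illustration of the mechanism, not an estimate.

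**The case against.** The strongest reply is that the documents give injection locations and nothing more. They do not mention needle size, visible marks or the usual dressings, and a small puncture may not be noticeable a day later. A mark also identifies the arm only to a parent who knows where each technique goes in. Section 9.0 says the study is explained before consent, but the consent form is not in the text reviewed, so what parents were told about sites or itching is unknown. All of this stands. It limits the claim to a blind that is open to failure and does not show that it fails.

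Second, side effects do not rest on the parent alone, because adverse events and rescue medication come from the chart. That stands too and reduces the exposure. It does not remove it, since untreated itching may leave no chart entry, and it does nothing for satisfaction.

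Third, dressings cannot hide itching, which Section 15.0 puts at 20% to 40% with ITM and which may itself suggest the arm. That is correct. It is a reason to ask parents for their guess, but not a reason to leave the avoidable route open.

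A reader might go further and infer any of the following, none of which the documents support:

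- **Parents will see the marks.** Visibility at 24 hours is an inference.
- **The interviewer will see them.** Section 10.0 has that person ask questions, not examine the child.
- **The side-effect hypothesis rests wholly on parental report.** Table 2 lists other sources.
- **The primary comparison is compromised.** MME/kg is taken from the chart, and the documents do not say that parents influence opioid dosing.
- **A bias of about 10 points is expected.** That figure follows only from assumed inputs.

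**Conclusion.** The point holds in a limited form. Sections 10.0 and 18.0 claim a blind for parent and child that, once the child is awake, has no described mechanism, although the two arms are injected at different sites. The two satisfaction items are fully exposed because the family is their only listed source. Parent-reported side effects are exposed in part. The primary outcome is not directly affected.

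The size of any bias cannot be derived from the documents. The firm figure is the granularity: 6.7 points in an arm's rate per changed answer, assuming a yes/no item and all 15 children in the arm analysed. The conclusion also assumes that marks or dressings could be noticed and linked to a technique, which is plausible but undocumented. The change is worth making because it is cheap and because, for side effects, the bias would favour one of the trial's two stated hypotheses.

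**What to change.** Add to Section 10.0:

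1. Every child, whichever block was given, leaves the operating room with identical opaque dressings over both flanks and the lumbar midline. They stay on until the 24-hour interview is finished unless a site needs inspection.
2. The interview ends by asking the parent which block they think was given. The answers are reported by arm. The question comes last so that it cannot colour the other replies.

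The cost is three dressings per child, one question and a short protocol addition, with no extra patients, visits or procedures. The downsides are small. A dressing may have to be lifted for inspection, and dressings do not stop a parent guessing from itching. The guess question helps to show how often parents identified the arm, though not by which route.

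If the sponsor prefers not to mask the sites, Sections 10.0 and 18.0 should limit the blinding claim to the data collector, and the satisfaction and parent-reported side-effect results should be reported as potentially unblinded. In either case, state whether the care team member used as fallback reporter is blinded.

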15.0 Risks to Subjects

- If a parent chooses for their child not to participate, the risk is the same since regional anesthesia is part of standard care at MUSC and will be offered regardless of study participation. Both study medications have been routinely used in practice at MUSC for over ten years.
- Subjects will be assigned to receive intrathecal morphine or a quadratus lumborum block by chance. One group may prove to be less beneficial than the other.
- Intrathecal Duramorph/Morphine: the use is well established in pediatric patients even though it is not FDA approved for use in children, but is commonly used in this population and at this institution for this indication. Other risks include infection at site of injection (less than 1%), damage to surrounding structures (less than 1%), block failure (1%) headache and cerebral spinal fluid leak (7%), Urinary retention (6%), Nausea and vomiting are the most common risks/side effects occurring in less than 10% of patients. Itching occurs in 20-40% of patients. Literature states that patients recover from side effects and are not long term.

QL Block/Ropivacaine: complications/risks are rare but include local anesthetic systemic toxicity (less than 0.01%), block failure (1%), bleeding and infection at block site (less than 1%), damage to surrounding structures (less than 1%), allergic reaction (rare, less than 1%), neurological complications (less than 1%). Literature states that patients recover from side effects and are not long term.

- There is a risk of loss of confidentiality.

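### When no parent is present, one input to the side-effect endpoint may come from a care-team member whose blinding the protocol does not state

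*Combined protocol and SAP*

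**What the plan says.** Section 10.0 sets the default source for side effects at about 24 hours: "a research team member will ask the parent/guardian about side effects such as nausea, vomiting, itching, etc". Table 2 in the same section lists the side effects experienced under a parent/guardian instrument at that time.

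The fallback has two parts. The first is "If a family member or guardian is not present, a care team member will be asked about side effects". The second, in the same sentence, is that the "chart will be reviewed for notes pertaining to side effects".

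On blinding, section 10.0 states: "The study team member who completes data collection from the family and chart review will be blinded to randomization". It adds that "the parent and child will also be blinded to the type of block that is used". Of the others it says: "The pharmacist will not be blinded to the randomization. Nor will the operative team". Section 18.0 repeats the same lists ("data collection from the family and chart review will be blinded to randomization, as well as the child and parent").

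Side effects are a secondary endpoint (section 4.0). The second hypothesis in the opening section on objectives is that they are more frequent with intrathecal morphine (ITM) than with quadratus lumborum (QL) blocks.

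**The concern.** The plan protects the side-effect interview by asking a blinded person. When no family member is there, the person who answers is someone for whom no blinding is stated. For a reported symptom it is the informant who judges whether it occurred and the interviewer who writes it down, so the interviewer's own blinding does not remove the problem.

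The expectation would run in one direction. For ITM, section 15.0 says "Itching occurs in 20-40% of patients" and also lists nausea and vomiting; its list for the QL block contains none of these. A clinician who knew the block would have reason to expect the queried symptoms in one arm only, which is the direction of the trial's own hypothesis. A staff member working a shift may also have seen only part of the 24 hours, so the substitute could differ from a parent in coverage as well as in blinding.

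At stake is how far the side-effect comparison can be described as blinded. No section provides for recording who the informant was, so the point could not be checked afterwards.

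**Working it through.** No figure in the plan is in dispute. The check sets the informant rule beside the blinding statements and then sizes the possible effect.

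**Step 1: who answers, and is that person blinded?** (sections 10.0 and 18.0)

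| Person | Part in the 24-hour side-effect item | Stated blinding |
|---|---|---|
| Parent/guardian | Default informant | Blinded |
| Data collector | Asks, records, reviews chart | Blinded |
| Care-team member | Informant if no family is present | Not stated |
| Operative team | Not named as informant, not excluded | Not blinded |

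The care-team role is not defined. The text therefore permits, but does not say, that the informant knows the block.

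**Step 2: weight of one child.** Sections 6.0 and 12.0 give 30 randomized, 15 per group. One child is 1/15 = 6.7 percentage points of an arm.

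**Step 3: how many children.** The documents do not give the share *f* of children with no family present. For illustration I assume 5% to 50%. Children per arm = 15*f*:
- 5%: 0.75
- 10%: 1.5
- 20%: 3.0
- 50%: 7.5

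**Step 4: spurious difference under moderate misreporting.** Let *b* be the net over-reporting among proxy-reported ITM children, with equal under-reporting among proxy-reported QL children. The spurious ITM minus QL difference is 2*fb*. If only the ITM arm is affected it is half that. Both *b* values are assumptions.

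| *f* | *b* = 0.10 | *b* = 0.20 |
|---|---|---|
| 5% | 1 point | 2 points |
| 10% | 2 points | 4 points |
| 20% | 4 points | 8 points |
| 50% | 10 points | 20 points |

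**Step 5: ceiling for false itching reports in the ITM arm.** A child who truly itches cannot be a false positive. With the true rate *p* at 20% to 40% (section 15.0), the expected ceiling is *f*(1 − *p*):
- *f* = 5%: 0.05 × 0.60 to 0.05 × 0.80 = 3 to 4 points
- *f* = 20%: 0.20 × 0.60 to 0.20 × 0.80 = 12 to 16 points

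Reaching it would need every itch-free proxy-reported child to be reported wrongly.

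**Step 6: what is out of reach.** Opioid use in the first 24 hours (the primary outcome in section 12.0) and the pain scores that section 4.0 adds to it are read from the chart, not from this interview.

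**The case against.** The strongest reply is that the protocol's silence about ward staff is not unblinding. Only the pharmacist and the operative team are named as unblinded, and nothing says that the care-team member asked was in the operating room or is told the arm. A reader might infer that the fallback informant is unblinded; the documents do not support that. What stands is the narrower point that the status is unstated and that operative-team members are not excluded.

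A reader might also infer that a blinded, parent-reported outcome is replaced by a verbal staff report alone. That is not so. The fallback includes chart review. Rescue medication for nausea or itching is taken from the administration record for all children. Table 2 has a separate side-effect and adverse-event row covering hours 0 to 48, and section 12.0 defines the outcome over 48 hours. The parent interview is one input among several. This objection stands and limits the weight of the point.

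Finally, it can be said that replacing the staff report with chart data alone would not cure the bias, because ward staff write the chart and give as-needed treatment, and mild untreated symptoms would be lost. That is also right: a ban on staff reports would be a trade-off, not a clear gain. It does not count against telephoning the parent first or recording the informant.

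**Conclusion.** The point holds as a minor gap in a stated source rule. For an unknown share of children, one input to a secondary endpoint with a directional hypothesis may come from someone who knows the block. I judge that share to be probably small, since the rule applies only when no family member or guardian is present, but the documents give no figure.

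The firm figure is 6.7 percentage points per affected child in a 15-child arm. Under the assumed ranges, moderate misreporting gives 1 to 8 points when 5% to 20% of children are proxy-reported. If few parents are absent, the effect may be nil. A reader might take the whole proxy share, 5 to 20 points, as the likely shift; that would require every proxy-reported ITM child to be symptom-free and reported as affected, which the protocol's own itching rate makes implausible.

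The primary outcome is not affected. This is a cheap improvement, not a threat to the trial's main conclusion.

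**What to change.** Amend the fallback in section 10.0 as follows:
- If the parent is not at the bedside, first put the same questions to the parent by telephone. Section 14.0 already describes the research team contacting the parent at about 24 hours and does not require that to be in person.
- Only if the parent cannot be reached, use chart review plus a care-team member who was not part of the operative team and has not been told the allocation.
- Record the informant for each child in REDCap.
- Repeat the side-effect comparison on parent-reported children only, as a sensitivity analysis.

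The cost is a few telephone calls, one data field and a smaller sample in the sensitivity analysis. Treatment, sample size and the primary analysis do not change. Some uncertainty remains for children whose parent cannot be reached, because the chart is also written by staff whose blinding is not stated; the source field at least shows how many such children there are.
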